## Summary

The outlook of a community-based intervention targeting nutrition and lifestyle behaviour modification among adults with metabolic syndrome (MetS) has not been fully explored. We describe the protocol of the development and three-month RCT of PERSUADE; a group-based community peer support intervention for Malaysian adults with MetS. The primary aim is to evaluate the effect of the peer support intervention on the clinical outcomes MetS components followed by improvements in the participants' dietary practices, physical activity levels and lifestyle behaviours. The PERSUADE module will be constructed using the Health Belief Model (HBM) to address relevant health messages from the appropriate guidelines and recent literature evidence on MetS among Malaysian adults. Following that, a minimum sample of 96 Malaysian adults with MetS will be randomised, either to the control group, who will receive one-time standard nutrition and lifestyle advice or the intervention group, who will participate in a three-month peer support program using the PERSUADE module. The participants will be followed up for three months post-intervention with data collection scheduled at baseline, 3-month and 6-month. PERSUADE is a peer support program developed with the aim improvement in nutrition and lifestyle behaviours among adults with MetS. The program constructed using information obtained from the published clinical and dietary guideline in Malaysia.

## Introduction

In Malaysia, non-communicable diseases such as cardiovascular diseases are the major cause of mortality, accounting for 70–80% of deaths, and its long-term complications are creating a major health burden for people by reducing the quality of life and increasing the healthcare cost to the society (1). Metabolic syndrome (MetS) is the clustering of three or more risk factors that increases the risk of developing type 2 diabetes and cardiovascular diseases and its increasing prevalence throughout the country is now recognized as a major health problem (2). The development of effective strategies for modifying antecedent conditions and risky behaviours, such as abdominal obesity, poor dietary habit and physical inactivity, is in a high priority to aid MetS management and prospective prevention endeavour in Malaysia.

There is a close relationship between MetS and poor lifestyle behaviour (3). Several lifestyle behaviours have been identified as predictors to MetS in Malaysia; poor dietary habit, food insecurity, poor food hygiene, physical inactivity and poor sleeping pattern (4). Hence, lifestyle intervention is seen as the most sustainable approach to the management and prevention step for MetS in Malaysia. However, there is currently only one lifestyle intervention studied among elderly with MetS (5) in Malaysia despite its increasing prevalence. Furthermore, a yearly increase in lifestyle-related non-communicable diseases in this country (4) calls for a need to develop a community-based campaign to promote an adoptable and sustainable healthy lifestyle program among Malaysian adults.

PERSUADE is a three months evidence-based community nutrition and lifestyle behaviour peer support program. The program brought together the existing clinical practice and medical nutrition therapy guidelines in the development process of its peer intervention modules. Furthermore, Health Belief Model (HBM) (6) will be incorporated in the content development of peer modules as its theoretical background. Consequently, the contents were further refined to suit local context using

input gathered from literature evidence synthesis and a qualitative study on motivation and barriers of healthy lifestyle. Eventually, the feasibility of this intervention is designed to be studied as a RCT for Malaysian adults with MetS with the aim to improve clinical outcome of MetS components. PERSUADE is aiming for an overall improvement in the MetS clinical outcomes in participants of the peer intervention group, besides investigating the impact of the peer intervention on the dietary practices, lifestyle behaviours, physical activity and health related quality of life.

## Methodology

### Study Design

This three-month RCT was designed to explore the feasibility of PERSUADE in community settings. The design was in accordance to the recommendations of the CONSORT statement for randomised trials of non-pharmacologic treatment (7). Based on Chronic Care Model (8) and the HBM (6) we developed a hypothetical framework of the study. This framework is constructed to form a theoretical design approach while addressing the patient activation concept in peer support (9) (Figure 1).

Four parent peer intervention modules are designed based on the information gathered from the published national practice guidelines and reported evidence of MetS in Malaysia. The flowchart detailing PERSUADE development and feasibility study is presented in Figure 2. The delivery of this intervention package through peer support program is expected to improve the clinical outcome of MetS components among participants' following their changes in dietary practices, physical activity levels and lifestyle behaviours. Furthermore, adoption of healthy dietary practices and lifestyle behaviours is expected to be reflected on the anthropometric outcomes and health related quality of life.

### Study Aims

The primary aim of our study is to evaluate the effect of a three-month peer support intervention on the clinical outcome of MetS components as compared to the control group. Furthermore, this study aims to determine the impact of the peer support intervention on dietary practices (nutrient intake, food frequency score), physical activity levels and lifestyle behaviours (smoking, alcohol consumption and sleeping habit) compared to the control group.

### Ethics Approval

The study has received ethics approval from Monash University Human Research Ethics Committee (CF16/56 - 2016000022).

## Study Sample

### Sample Size and Power Calculation

The estimated sample size based on earlier similar study (10) on one the study variables, fasting plasma glucose at 95% confidence and 80% power of an anticipated fall in FPG of 1.5 to 1.8 mmol/L. Using an equation to detect changes in a standard parallel-group trial and a 20% drop out rate, the calculated minimum required sample size is 48 participants for each group thus the totalling 96 for both randomized arm.

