### Recruitment Process

A series of health screening camp were organised around Kulai district located in the south of Malaysia. Johor state was specifically selected due to high prevalence of MetS as reported in Malaysia Adults Nutrition Survey (MANS) (11) (12), Metabolic Syndrome Study Malaysia (MSSM) (13) and National Health and Morbidity Survey 2015 (NHMS) (14). The eligibility screening and recruitment of study participants were conducted in four low to middle income neighbourhoods. The research team provide assistance on identifying potential study participants according to the eligibility criteria (Table 1). If an individual is found to eligible to participate, they will be requested to complete the baseline questionnaire after consenting for their participation.

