### Randomisation and Treatment Allocation

Eligible adults who have consented to participate are matched for age, sex and ethnicity as baseline. To minimised contamination, participants were randomised to either intervention or control group based on their location.

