### *Intervention Group*

Participants residing in the location selected to be intervene will to form at minimum 4 peer groups. This group will receive a continuous three-months, peer-led nutrition and lifestyle behaviour intervention through a series of peer gathering. Two participants from each peer group will be selected as the peer leader (PL). PL will be trained to deliver the content of PERSUADE modules and will be responsible to run a weekly peer gathering with their respective groups for the following three months.

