## Randomisation and Blinding

This study is an open label parallel randomized-controlled trial hence both the research team and participants will not be blinded. However, as the randomisation will be made based on participants location, contamination of participants was minimised.

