### Peer Leader Selection

As an elaboration to the study flowchart (Figure 2), the intervention group will form a minimum number of eight peer groups with two PL will be selected from each group on voluntarily basis. PL will be trained for the all four modules and an extra module; health promotion. This module aimed at assessing appointed PL for leadership, health educator role, and understanding of the PERSUADE modules. All PL attended a two-days training session on focussing on leadership and communication skills. On top of that, a practical approach will be used, including physical, nutritional, and psychological aspects of a lifestyle change as included in all four PERSUADE modules. PL will be trained to engage with their peers in conversations about the issues of concern, seeking to promote health-enhancing knowledge and skills. The goal for each peer group is to be able to identify potential barriers and determinants of lifestyle improvement and subsequently take actions to reduce their CVD risk. At the end of PL training, a simple post-questionnaire will be distributed among them to indicate validity and adequateness of their knowledge and skills on all peer modules.

Respective PL will distribute the posters among their peer group every week to initiate discussion of relevant topics based on the weekly objectives. In order to maximise the participation, regular reminder about the next peer gathering sessions and short health message through text were regularly sent by PL. Peers will then have to keep the poster and returned it to the PL at the end of three months as a measure of compliance to the peer support program. Besides, peers are also encouraged to distribute the poster as a health promotion steps among the community.

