### Statistical Analysis

Diet and nutrition data will be analysed using Axxya Systems Nutritionist Pro™ Diet Analysis while all statistical analyses are performed with IBM® SPSS® Statistics 23.0. Descriptive methods will be used to demonstrate to describe participant characteristics and the consistency of both groups. Independent t-test or Chi Square will be used to evaluate baseline characteristics of peer intervention

participants compared to control, overall significance of improvement across clinical outcome measures. As this is a RCT involving repeated measures, the ANOVA repeated measures model is applied to observe significant differences between and within the study groups. This includes change in clinical measures of MetS component from baseline, end of trial (3rd month) and follow up (6th month). The magnitude of change in both primary and secondary outcome measures will be estimated and the given 95% confidence intervals with the p value 0.05 was taken as the level of significance.

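### The 80% power stated for 48 per arm is not supported for a trial allocated by location, and the planned analysis has no term for location

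*Combined protocol and SAP*

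**What the plan says.** Sample Size and Power Calculation sizes the trial on fasting plasma glucose (FPG), with "95% confidence and 80% power of an anticipated fall in FPG of 1.5 to 1.8 mmol/L". The method is described as "Using an equation to detect changes in a standard parallel-group trial and a 20% drop out rate", and the result is 48 per arm, 96 in all.

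The allocation unit is given elsewhere. Randomisation and Treatment Allocation says "participants were randomised to either intervention or control group based on their location", and Randomisation and Blinding repeats it: "as the randomisation will be made based on participants location, contamination of participants was minimised". Recruitment Process adds: "The eligibility screening and recruitment of study participants were conducted in four low to middle income neighbourhoods".

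The intervention is delivered in peer groups, and two sections give different minimum numbers. Intervention Group says "Participants residing in the location selected to be intervene will to form at minimum 4 peer groups", while Peer Leader Selection says "the intervention group will form a minimum number of eight peer groups".

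For the analysis, Statistical Analysis says "the ANOVA repeated measures model is applied to observe significant differences between and within the study groups". It names no term for location or peer group and does not say which ANOVA term or visit carries the primary conclusion.

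**The concern.** A standard parallel-group equation treats participants as independent. People allocated together because they live in the same place tend to have correlated outcomes, and the evidence about treatment then rests largely on how many locations there are. The sample size section allows for dropout and nothing else.

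Two things are at stake. First, Study Aims makes the effect on clinical outcomes primary, so a null result could be taken as coming from an adequately powered trial when that has not been shown. Second, with no location term, a difference between neighbourhoods can be reported as a treatment effect, and the nominal 5% level no longer holds.

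**Working it through.** **Inputs from the documents:** 80% power, 95% confidence (taken as two-sided 0.05), 48 per arm, 20% dropout, allocation by location, four neighbourhoods in total.

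**Not in the readable text:** the SD of FPG, the ICC, and how the locations divide between arms.

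**Assumed for illustration:** two locations per arm, ICC 0.01/0.02/0.05 and, where needed, a within-person correlation of 0.5.

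**1. The plan's own figure.** 48 × 0.8 = 38.4, so 38 evaluable per arm. A two-sample t-test with 38 per arm has 80% power at a standardised difference d = 0.651. If the stated fall is a between-arm difference, the implied SD is 1.5/0.651 = 2.30 or 1.8/0.651 = 2.76 mmol/L. The document gives no SD to compare with these, so 48 can be neither confirmed nor refuted.

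**2. Power with location taken into account, unadjusted single-visit comparison.** Each location has 38/2 = 19 evaluable people.
- Design effect = 1 + (19 − 1) × ICC. The effective number per arm is 38 divided by this, with the t-test degrees of freedom (df) based on that effective number.
- Location-level test: variance of a location mean = ICC + (1 − ICC)/19 in SD² units, and 2 × (2 − 1) = 2 df, using the noncentral t.

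| ICC | Design effect | Power by design effect, d = 0.651 | Power on 2 df, d = 0.651 | Power by design effect, d = 1.0 | Power on 2 df, d = 1.0 |
|---|---|---|---|---|---|
| 0 | 1.00 | 80% | 36% | 99% | 62% |
| 0.01 | 1.18 | 73% | 32% | 98% | 57% |
| 0.02 | 1.36 | 67% | 29% | 96% | 52% |
| 0.05 | 1.90 | 52% | 23% | 87% | 42% |

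The ICC 0 row shows that most of the loss in the 2-df columns comes from having only four locations.

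**3. Baseline adjustment.** If the implied SD is a single-visit SD, adjusting for baseline at correlation 0.5 multiplies the variance by 1 − 0.5² = 0.75, so d becomes 0.651/√0.75 = 0.752. Applying the same ICCs to the residual, power is 84/79/64% by design effect and 39/35/28% on 2 df. If the SD was already one of change, this gain does not apply.

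**4. Type I error with no location term** (simulation, 2:2 locations, 19 each). A single-visit t-test rejects 7/9/16% of the time at ICC 0.01/0.02/0.05. For three-visit repeated measures ANOVA at ICC 0.05 and within-person correlation 0.5:

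| Share of location variance stable over time | Group-by-time term | Between-group term |
|---|---|---|
| 100% | 5% | 21% |
| 80% | 11% | 19% |
| 50% | 21% | 16% |

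All these tests sit at about 5% when the ICC is 0. The inflation depends on which term is tested and on how stable the location differences are.

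**5. Peer groups.** With no location effect, d = 0.651 and ICC 0.05 within peer groups in the intervention arm only, power is about 72% with 4 groups and 76% with 8. The unreconciled minimum therefore matters too, though less than location.

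**The case against.** Several points on the other side are fair.

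- **Feasibility.** Study Design and the closing discussion call this a feasibility study, which could excuse loose sizing. But Study Aims makes efficacy primary, and the plan attaches a power figure and a significance level to it.
- **Matching.** Participants are matched on age, sex and ethnicity, which may narrow differences between locations. It does not remove correlation within a location or add locations.
- **The missing inputs may exist.** The SD, and the meaning of the fall, may be in the cited earlier study, and the split of locations may be in Figure 2, which is not shown here. This stands: one can say only that they are not in the readable text. Neither source would change the fact that the section describes an allowance for dropout alone.
- **The low powers owe much to the method.** The 2-df figures reflect the number of locations more than the ICC, and they assume a 2:2 split with neighbourhoods as the allocation units. The singular wording under Intervention Group would also fit one location per arm, where no such test exists. This stands, and so does the point that baseline adjustment can bring design-effect power above 80% at ICC 0.01.

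A reader might also infer that 48 is miscalculated. The documents do not support that: the implied SDs of 2.30 to 2.76 mmol/L cannot be checked. Whether the fall of 1.5 to 1.8 mmol/L is a between-arm difference is an ambiguity, not a demonstrated error.

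**Conclusion.** The concern holds as a mismatch between design, sample size and analysis. The 80% comes from an equation for independent participants, allocation is by location, and the analysis has no location term. That conclusion needs no assumed ICC.

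The size of the effect does need assumptions. Under those above, and if the true effect is near d = 0.651, power falls to 52–73% by design effect or 23–32% on 2 df without baseline adjustment. With adjustment it is 64–84% or 28–39%. Type I error with location ignored ranges from 5% to 21% across the cases examined.

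It is tempting to conclude that the trial's power is about 30%, or that it is certainly below 80%. Neither follows. With a larger true effect such as d = 1.0, design-effect power stays at 87% or more over the same ICCs, and true power cannot be stated without the SD, the ICC and the locations per arm.

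**What to change.** Keep the minimum of 96.

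**Sample Size and Power Calculation**
- Describe the trial as location-randomised and state the number of locations per arm.
- Give one between-arm FPG difference with its SD and source, and say whether that SD is for a single visit, for change, or baseline-adjusted.
- Replace the unconditional 80% with power over a stated, assumed ICC range, computed for the analysis actually planned and with small-cluster degrees of freedom.

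**Statistical Analysis**
- Specify a baseline-adjusted analysis that accounts for location. Apply it to all the primary outcomes listed under Metabolic Syndrome Biomarkers, not to FPG alone.
- Name the term and visit tested, and report estimates with confidence intervals.
- If there is one location per arm, state that the treatment effect cannot be separated from location.

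**Peer groups:** reconcile the minimum of 4 under Intervention Group with the minimum of 8 under Peer Leader Selection.

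**Cost:** one section is rewritten, the analysis model is replaced, and a sourced SD and an ICC range must be found. No further participants are required. Stated power becomes less favourable and intervals widen: with two locations per arm, the multiplier is t = 4.30 on 2 df instead of 1.99 on 74 df.

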### Recruitment Process

A series of health screening camp were organised around Kulai district located in the south of Malaysia. Johor state was specifically selected due to high prevalence of MetS as reported in Malaysia Adults Nutrition Survey (MANS) (11) (12), Metabolic Syndrome Study Malaysia (MSSM) (13) and National Health and Morbidity Survey 2015 (NHMS) (14). The eligibility screening and recruitment of study participants were conducted in four low to middle income neighbourhoods. The research team provide assistance on identifying potential study participants according to the eligibility criteria (Table 1). If an individual is found to eligible to participate, they will be requested to complete the baseline questionnaire after consenting for their participation.

### Randomisation and Treatment Allocation

Eligible adults who have consented to participate are matched for age, sex and ethnicity as baseline. To minimised contamination, participants were randomised to either intervention or control group based on their location.

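### Matching on age, sex and ethnicity is undefined relative to allocation by location, and the planned analysis does not use those three factors

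*Combined protocol and SAP*

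**What the plan says.** Two consecutive sentences under Randomisation and Treatment Allocation describe how the arms are formed. The first is "Eligible adults who have consented to participate are matched for age, sex and ethnicity as baseline". The second states that "participants were randomised to either intervention or control group based on their location".

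Other sections confirm that arm follows residence. Randomisation and Blinding says "as the randomisation will be made based on participants location, contamination of participants was minimised", and Intervention Group says "Participants residing in the location selected to be intervene will to form at minimum 4 peer groups". Recruitment Process gives the number of places: "recruitment of study participants were conducted in four low to middle income neighbourhoods". The split of the four between arms is not stated.

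On the analysis side, the Statistical Analysis section says "Independent t-test or Chi Square will be used to evaluate baseline characteristics of peer intervention"; the rest of that sentence also mentions improvement in clinical outcomes. It then says "the ANOVA repeated measures model is applied to observe significant differences between and within the study groups", and adds that this covers change from baseline to months 3 and 6. It names no covariate, no pair or stratum term and no location term. Baseline differences are to be tested, but no action is stated if they are found.

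**The concern.** Matching is the only device the plan offers for balancing age, sex and ethnicity, yet the reader cannot tell what it is. No ratio or tolerance is given, nor what happens to people without a match. The plan also does not say whether matching is finished before the locations are allocated. In an open-label trial that order matters: choosing participants once arms are known is a different procedure from forming comparable samples beforehand.

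With only four units to allocate, chance cannot be relied on to even out these factors. Whatever the matching achieves, the analysis makes no use of it. Depending on what was done, the result could be intervals that are too wide, a confounded comparison, or simply lost precision. These consequences are alternatives, and they do not all point the same way.

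**Working it through.** **The plan's own figure.** Sample Size and Power Calculation rests on "fasting plasma glucose at 95% confidence and 80% power of an anticipated fall in FPG of 1.5 to 1.8 mmol/L", a standard parallel-group equation and 20% dropout, giving 48 per group. No SD is stated, so 48 cannot be rebuilt forwards. Working back: 38/(1 − 0.2) = 47.5, rounded up to 48. (40 × 1.2 = 48 is the other route.) With 38 evaluable per arm, two-sided 5% (sidedness assumed) and 80% power, the detectable standardised difference is (1.960 + 0.842) × √(2/38) = 0.643. The implied SD is then 1.5/0.643 = 2.33 or 1.8/0.643 = 2.80 mmol/L. This formula is unmatched, so matching plays no part in the sample size either.

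**Matching against allocation.** If pairs span locations in different arms, each member's arm is fixed by residence, so no draw takes place within the pair. If pairs lie within one location, both members share an arm. Either way, random assignment within pairs is not possible. Matching could still make the arms similar if done by frequency or by choosing similar locations. The text does not say which is meant.

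**Case A: pairs are real and ignored.** With n pairs and within-pair correlation r, the true variance of the difference in means is 2σ²(1 − r)/n; the unpaired analysis uses 2σ²/n. The interval is too wide by 1/√(1 − r), and the actual type I error is 2[1 − Φ(1.960/√(1 − r))]. The correlations are assumed, and clustering by location is set aside.

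| r (assumed) | Width ratio | Actual type I error |
|---|---|---|
| 0.1 | 1.054 | 0.039 |
| 0.2 | 1.118 | 0.028 |
| 0.3 | 1.195 | 0.019 |

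At the effect for which the trial has 80% nominal power, power over this range is 0.81-0.84 unpaired and 0.84-0.92 paired. The error is conservative and wasteful.

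**Case B: balance is not achieved.** Let one level of a factor be more common in one arm by a proportion p. Let it shift the outcome by a at every visit, and by a further c at follow-up. With true effect δ, the arm difference is p·a at baseline and δ + p·(a + c) at follow-up. The difference in change is δ + p·c. A stable level difference cancels; only c, the factor's association with change, biases the contrast. Neither p nor c is in the documents, so the size of the bias cannot be derived.

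**Case C: frequency matching succeeds.** Confounding by these three factors is then largely removed without adjustment. Adjusting still scales the standard error by √(1 − R²), where R² is the share of variance explained (assumed). At 10% this is √0.90 = 0.949, about 5% smaller; at 20% it is √0.80 = 0.894, about 11% smaller.

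**The case against.** Four stronger readings are tempting, and the documents do not support them.

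- **A reader might infer that matching and allocation by location are incompatible.** The text says that adults are matched, without saying at what level. Frequency matching across neighbourhoods, or matching of the locations themselves, fits with allocation by location. The procedure is undefined, not impossible. The trial flow chart (Figure 2) is not reproduced in the available text, and it may or may not show the sequence.
- **A reader might infer that consented people must be dropped once their arm is known.** Recruitment Process and the allocation section read most naturally as consent and baseline questionnaire, then matching, then allocation. Comparable samples could be formed before the locations are drawn. The timing is not fixed, so selection after allocation is a possibility to rule out, not a finding.
- **A reader might conclude that the intervals are wrong whatever was done.** Case A is conservative. Case C leaves the comparison largely free of confounding by these three factors, though not by other differences between locations.
- **A reader might put a number on the confounding by multiplying an imbalance by an ethnic difference in outcome level.** That does not fit a comparison of change, as Case B shows. The protocol's remark about differences across racial populations (Community-relevant Approach) has an unclear referent and concerns module content, so it is weak evidence that ethnicity predicts change.

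It is also fair to object that four allocated locations with no clustering term is the larger problem, and that covariates do not cure it. That stands, and this point does not claim otherwise. What remains is that the plan relies on three factors for balance and then leaves them out of the comparison, and that they can be included at almost no cost.

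**Conclusion.** The point holds as a gap in specification with an inexpensive remedy. The plan does not define the matching or place it in time relative to allocation, and does not carry the matching factors into the analysis.

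The consequence depends on what was actually done:

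- **Real pairs:** intervals about 5-20% too wide, in the conservative direction, at assumed correlations of 0.1-0.3.
- **Failed balance:** possible confounding of the difference in change, of unknown size.
- **Successful frequency matching:** a standard error reduction of about 5-11% forgone, at an assumed 10-20% of variance explained.

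Every percentage here rests on an assumed correlation or R², none of which the documents give. The change is worth making because it helps in each case, and the documents do not reveal which case applies.

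**What to change.** **Statistical Analysis.** Pre-specify, for each clinical outcome at 3 and 6 months, a between-arm model that adjusts for the baseline value of that outcome, age, sex and ethnicity. If pairs or strata are actually formed, include a pair or stratum term instead.

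**Randomisation and Treatment Allocation.** State the level and method of matching, that it is completed before locations are allocated, and that no consented participant is dropped afterwards to create a match. Part of that section is in the past tense; if allocation has already happened, report the sequence that was followed.

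**What to avoid.** Do not add location as a fixed effect. It is nested in arm, so the arm effect could not be estimated. Four allocated locations analysed without clustering is a separate problem that must be handled on its own; these covariates do not correct it.

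**Cost.** One degree of freedom each for baseline, age and sex, plus one fewer than the number of ethnic groups. With an assumed two to four groups this is 3 + 1 to 3 + 3, or four to six, from 76 (2 × 38) to 96 participants. No new data collection is needed: Table 3 lists age and ethnicity, and sex, which it does not list, has to be recorded in order to match on it.
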